4.1.1. Dose Escalation Phase

Phase 1a (dose escalation) will assess the safety and tolerability of LY3435151 to identify a monotherapy recommended phase 2 dose (RP2D) and a combination RP2D in patients with solid tumors associated with TIL positivity:

- TNBC
- Gastric adenocarcinoma (including gastroesophageal junction)
- HNSCC
- Squamous cervical carcinoma
- High-grade serous ovarian carcinoma
- HCC
- UPS and LMS.

Patients enrolled in Part A (Cohorts A1 through A6) will receive LY3435151 monotherapy. Patients enrolled in Part B (Cohorts B1 and B2) will receive LY3435151 and pembrolizumab.

The RP2D will be determined based on the number of observed dose-limiting toxicities (DLTs) and PK/pharmacodynamic (PD) data, and may be below the maximum tolerated dose (MTD), which may not necessarily be reached during the dose escalations. The dose-escalation phase will employ a modified toxicity probability interval (mTPI-2) method and starting with Cohort A2 will enroll at least three evaluable patients per cohort. Treatment cycles will consist of 21 days. A 2-cycle DLT observation will apply to all cohorts in Phase 1a. Refer to Section 4.1.1.1 for additional details on the dose escalation method.

A minimum of 1 patient will be enrolled in Cohort A1 and will receive a 10-mg dose. If the 10-mg dose level DLT period is cleared, Cohort A2 (30-mg dose level) will be initiated.

If a patient in Cohort A1 experiences a DLT, additional patients will be enrolled into Cohort A1 following the mTPI-2 method. Based on the mTPI-2 method, at least additional 4 patients will need to be enrolled and experience no DLT during the DLT observing period before escalating to the next dose level (Cohort A2).

After the first patient in Cohort A2 receives the first dose of LY3435151, there will be a delay of 1 week before the second patient receives LY3435151 to allow for safety observation. In all subsequent cohorts, the first patient in each dose level will be observed for at least 24 hours before treatment of additional patients; no additional delays are required for subsequent patients.

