6.6. Dose Modification

Dose reductions are not allowed in this study.

No dose modification for either LY3435151 or pembrolizumab (delays or omissions greater than 14 days) is allowed during the DLT observation period (42 days for Cohorts A1-A6 and B1-B2). Starting at Cycle 3, dose delays will be permitted. See Section 7 for discontinuation criteria.

After the DLT observation period, doses of the LY3435151 or pembrolizumab may be delayed, omitted, or discontinued to manage specific AEs or other toxicities. All dose modifications should be documented, including the approach taken and a clear rationale for the need for modification. The investigator must assess whether the toxicity is at least possibly due to study treatments and apply the dose modification guidelines. Investigators are encouraged to consult Lilly for additional guidance.

A cycle is defined as an interval of 21 days as shown in the SoA (Section 1.3). A delay of a cycle due to holiday, weekend, bad weather, or other unforeseen circumstances will be permitted for a maximum of 7 days and not counted as a protocol deviation. The reason for the delay should be documented on the eCRF.

Starting at Cycle 3, if a patient requires a cycle delay for any safety reasons other than those above, study treatment should be resumed within 21 days, if possible and appropriate. In rare circumstances, a cycle delay of >21 days may be permitted before permanent treatment discontinuation, as long as the patient demonstrates clinical benefit, does not have objective progression, and is recovering from the toxicity. Longer delays may be allowed for irAEs, as described in Section 6.6.1. Such circumstances must be discussed with the Lilly CRP/CRS.

Adverse events of immune-related etiology are expected because of the study drug's mechanism of action and may occur shortly after the first dose or several months after the last dose. Study treatment must be withheld if the patient experiences a drug-related toxicity or a severe or life-threatening AE.

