A 4-hour observation period from the end of LY3435151 administration will occur in Cycles 1 and 2. During the observation period, patients treated with LY3435151 should be closely monitored for signs and symptoms indicative of an IRR by medical staff from the start of the infusion, in an area where emergency medical resuscitation equipment and other agents (eg, epinephrine, prednisolone, or equivalents) are available. LY3435151 IRRs will be defined according to the Common Terminology Criteria for Adverse Events (CTCAE), version 5.0 definition of IRRs.

The table below presents instructions for management of infusion-related reactions associated with LY3435151, pembrolizumab, or combination therapy.

Management of Infusion-Related Reactions

NCI CTCAE Grade	Treatment	Premedication at Subsequent Dosing

Grade 1
 
Mild reaction; infusion interruption not indicated; intervention not indicated
	
 Increase monitoring of vital signs as medically indicated until the participant is deemed medically stable in the opinion of the investigator. 	
None

Grade 2
 
Requires therapy or infusion interruption but responds promptly to symptomatic treatment (e.g., antihistamines, NSAIDs, narcotics, IV fluids); prophylactic medications indicated for ≤24 hrs.
	
 Stop Infusion. Additional appropriate medical therapy may include but is not limited to: 
 IV fluids Antihistamines NSAIDs Acetaminophen Narcotics Increase monitoring of vital signs as medically indicated until the participant is deemed medically stable in the opinion of the investigator. If symptoms resolve within 1 hour of stopping drug infusion, the infusion may be restarted at 50% of the original infusion rate (e.g. from 100 mL/hr. to 50 mL/hr.). Otherwise dosing will be held until symptoms resolve and the participant should be premedicated for the next scheduled dose. 
Participants who develop Grade 2 toxicity despite adequate premedication should be permanently discontinued from further study drug treatment
	
Participant may be premedicated 1.5 h (± 30 minutes) prior to infusion of LY3435151 or pembrolizumab with:
 
Diphenhydramine 50 mg PO (or equivalent dose of antihistamine).
 
Acetaminophen 500 to 1000 mg PO (or equivalent dose of analgesic).

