
Grades 3 or 4
 
Grade 3: Prolonged (i.e., not rapidly responsive to symptomatic medication and/or brief interruption of infusion); recurrence of symptoms following initial improvement; hospitalization indicated for other clinical sequelae (e.g., renal impairment, pulmonary infiltrates)
 
Grade 4: Life-threatening; pressor or ventilator support indicated
	
 • Stop Infusion. • Additional appropriate medical therapy may include but is not limited to: 
 • Epinephrine** • IV fluids • Antihistamines • NSAIDs • Acetaminophen • Narcotics • Oxygen • Pressors • Corticosteroids • Increase monitoring of vital signs as medically indicated until the participant is deemed medically stable in the opinion of the investigator. • Hospitalization may be indicated. 
**In cases of anaphylaxis, epinephrine should be used immediately.
 
Participant is permanently discontinued from further study drug treatment.
	
No subsequent dosing

Appropriate resuscitation equipment should be available at the bedside and a physician readily available during the period of drug administration. For further information, please refer to the CTCAE v5.0 at http://ctep.cancer.gov
		

If an IRR is clearly attributable to only one of the drugs, then the patient may continue to receive the other drug after consultation with the sponsor.

6.6.1. Dose Modification and Toxicity Management for Immune-Related AEs Associated with LY3435151, Pembrolizumab, or Combination Therapy

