6.6.3. Other allowed dose interruption for pembrolizumab

Pembrolizumab may be interrupted for situations other than treatment-related AEs such as medical / surgical events or logistical reasons not related to study therapy. Participants should be placed back on study therapy within 3 weeks of the scheduled interruption, unless otherwise discussed with the Sponsor. The reason for interruption should be documented in the patient's study record.

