9.3. Populations for Analyses

For purposes of analysis, the following populations are defined:

Population	Description
Enrolled	All participants who sign informed consent
Biomarker	All enrolled patients from whom a valid assay result has been obtained
Pharmacokinetic	All enrolled patients who have received ≥ 1 full dose of LY3435151 and have baseline and ≥ 1 postbaseline evaluable PK sample
Safety	All enrolled patients who have received ≥ 1 dose of study treatment, regardless of their eligibility for the study. The safety population will be used for all dosing/exposure and safety analyses.
DLT-evaluable	All treated patients who have completed 2 cycles (6 weeks) of treatment (having taken at least 75% of the planned doses of LY3435151) or have discontinued treatment due to a DLT.

Abbreviations: DLT = dose-limiting toxicity; PK = pharmacokinetics.

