5.4.1. Analysis Population

For purposes of analysis, the following populations are defined:

Population	Description
Enrolled	All participants who sign informed consent
Biomarker	All enrolled patients from whom a valid assay result has been obtained
Pharmacokinetic	All enrolled patients who have received ≥ 1 full dose of LY3435151 and have baseline and ≥ 1 postbaseline evaluable PK sample
Intent-to-Treat	All patients who are randomized (enrolled) to study treatment. Patients will be grouped according to randomized treatment. This ITT population will be used for all baseline and efficacy analyses.
Safety	All randomized (enrolled) patients who have received ≥ 1 dose of LY3435151, regardless of their eligibility for the study. Patients will be grouped according to treatment received in Cycle 1. The safety population will be used for all dosing/exposure and safety analyses.
DLT-evaluable	All treated patients who have completed 2 cycles (6 weeks) of treatment (having taken at least 75% of the planned doses of LY3435151) or have discontinued treatment due to a DLT.

Abbreviations: DLT = dose-limiting toxicity; ITT = intent-to-treat; PK = pharmacokinetics.

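### The DLT-evaluable set requires LY3435151 exposure only, so a Part B patient who misses pembrolizumab for a non-DLT reason still counts as a DLT-free combination patient

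*Protocol*

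**What the plan says.** Protocol 9.3 counts as DLT-evaluable "All treated patients who have completed 2 cycles (6 weeks) of treatment (having taken at least 75% of the planned doses of LY3435151"), together with patients who discontinued because of a DLT. SAP 5.4.1 has the same test, "having taken at least 75% of the planned doses of LY3435151", and no separate rule for Part B.

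Four other provisions matter here.

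- **Window.** Protocol 4.1.1: "A 2-cycle DLT observation will apply to all cohorts in Phase 1a". That section also gives Part B patients both drugs, every 3 weeks.
- **Cycle.** Protocol 6.6: "A cycle is defined as an interval of 21 days as shown in the SoA". A cycle is a span of time, not receipt of both drugs.
- **Interruption of pembrolizumab.** Section 6.6 rules out modification of either drug in the window. The sentence begins with the word No, runs on to "delays or omissions greater than 14 days) is allowed during the DLT observation period", and names Cohorts B1 and B2. Section 6.6.3 permits pembrolizumab interruptions for medical, surgical or logistical reasons without exempting the window: "Participants should be placed back on study therapy within 3 weeks of the scheduled interruption, unless otherwise discussed with the Sponsor".
- **Infusion reactions.** Section 6.6: "Participants who develop Grade 2 toxicity despite adequate premedication should be permanently discontinued from further study drug treatment". It adds: "If an IRR is clearly attributable to only one of the drugs, then the patient may continue to receive the other drug", after consulting the sponsor.

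Appendix 6 bases the final MTD on the number of DLTs and the number of DLT-evaluable patients.

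**The concern.** Part B is meant to find a tolerable LY3435151 dose given with pembrolizumab. A patient who received less than the planned pembrolizumab says less about that, yet the set gives the patient full weight in the denominator. Protocol 2.3 acknowledges that the combination may make toxicities such as immune-related events more frequent or more severe, so the expected error is a combination DLT rate that is too low. Part B plans about 6 to 8 patients over two levels, so one patient is a quarter to a third of a cohort. At stake are the decision to move from B1 to B2 and the choice of the combination RP2D.

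**Working it through.** **1. What the definition requires.** In 42 days of 3-weekly dosing, 2 doses of each drug are planned. For LY3435151, 0.75 × 2 = 1.5, so both doses are needed. For pembrolizumab nothing is required.

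**2. Whether such a patient can arise.**

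- *Non-AE interruption (6.6.3).* Three weeks is a full cycle and exceeds the 14 days in 6.6, so the two sections conflict within the window. No adverse event is involved, so the DLT criterion in 4.1.1.2 for an AE-caused treatment delay over 14 days does not apply. A breach of 6.6 would be a conduct deviation. Neither document says that it removes the patient from the set.
- *Repeat Grade 2 infusion reaction.* Pembrolizumab alone may be stopped if the reaction is clearly attributable to it. Grade 2 is not in itself a listed DLT, but the AE-delay criterion, or the criterion for toxicity that the investigator and sponsor judge dose-limiting, may apply. If either does, the patient is not DLT-free and the gap does not arise.

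Premedication applies from the next dose, so a reaction despite premedication comes at Cycle 2 Day 1 at the earliest. Section 6.6.3 normally returns the patient within one cycle. Both routes therefore usually lose about one of two doses.

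**3. Reproducing the decision rule.** I used mTPI-2 with target 0.30, interval 0.25-0.35, a Beta(1,1) prior, sub-intervals of width 0.10, and DU if P(rate > 0.30) > 0.95. The prior and the 0.95 cut-off are my assumptions. The rule reproduces every stated example: 1/3 S, 1/6 E, 2/3 D and 5/7 DU (Appendix 6), and 2/6 S (4.1.1.1). It also gives 1/4 S and 1/5 E, matching the four further DLT-free patients that 4.1.1 requires after a DLT in the first A1 patient.

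**4. Effect of leaving out one DLT-free patient with inadequate pembrolizumab.**

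| Counted | Decision | Without that patient | Decision |
|---|---|---|---|
| 0/3 | E | 0/2 | below the three-evaluable minimum |
| 1/5 | E | 1/4 | S |
| 2/6 | S | 2/5 | D |
| 0/4 | E | 0/3 | E (no change) |
| 1/4 | S | 1/3 | S (no change) |

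The first row relies on the minimum in 4.1.1, stated for the escalation phase from Cohort A2 onward, which I read as covering Part B. Section 4.1.1.1 repeats it for A2 to A6 only. Without a minimum, the rule reads E at 0/2. Counts of 5 or 6 arise only if a cohort is extended beyond the planned 3 to 4.

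**5. Chance of reading 0/3, given one such patient.** Let p be the true combination DLT rate and m the risk of the under-exposed patient, both assumed. With three fully exposed patients the chance is (1 − p)³; with one under-exposed it is (1 − p)² × (1 − m).

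| p | All three exposed | One with m = 0.20 to 0.05 |
|---|---|---|
| 0.30 | 0.7³ = 0.343 | 0.49 × 0.80 to 0.49 × 0.95 = 0.39 to 0.47 |
| 0.40 | 0.6³ = 0.216 | 0.36 × 0.80 to 0.36 × 0.95 = 0.29 to 0.34 |
| 0.50 | 0.5³ = 0.125 | 0.25 × 0.80 to 0.25 × 0.95 = 0.20 to 0.24 |

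**6. Averaged over the chance q that a patient misses pembrolizumab.** With p = 0.40 and m = 0.10, the chance is [(1 − q) × 0.60 + q × 0.90]³.

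- q = 0.05: (0.570 + 0.045)³ = 0.615³ = 0.233
- q = 0.10: (0.540 + 0.090)³ = 0.630³ = 0.250

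Against 0.216, the rise is about 0.02 to 0.03.

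**The case against.** The best defence is that completing two cycles of treatment in Part B already means both drugs, since the Schedule of Activities places pembrolizumab on Day 1 of Cycles 1 and 2, and that the specific bar in 6.6 prevails over the general allowance in 6.6.3. That is a reasonable account of the intent. It does not settle evaluability, because a cycle is defined as an interval, the only exposure test names one drug, and the bar in 6.6 carries no consequence for the analysis set. The review in 4.1.1.2 that can make a case not evaluable concerns potential DLTs, not DLT-free patients with too little exposure.

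Two stronger readings are tempting. A reader might infer that Part B would rest on patients treated essentially with monotherapy. The wording does admit zero pembrolizumab doses, but the routes in the protocol usually cost about one dose of two, and an AE-caused delay over 14 days is already a DLT. A reader might also infer that one miscount fixes the dose for all of Part D, about 40 + 40 + 30 = 110 patients. The documents do not support that. They provide sponsor-investigator review after each cohort (4.1.1), room for a more conservative choice (4.1.1.1), re-evaluation at a 30% cumulative incidence of DLT-equivalents (4.1.1.3), RP2D selection on the totality of data (4.1.1.4), an interim analysis before expansion (4.1.2), possible RP2D revision (9.2), and a review at about 20 patients in each of D1 and D2 (9.5). These limit the harm, but they are partly discretionary and do not correct the count.

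**Conclusion.** The point holds. As written, the set counts a Part B patient with inadequate pembrolizumab exposure, for a reason that is not a DLT, as a DLT-free combination patient. One such patient can turn a stay, or a cohort not yet ready for a decision, into an escalation at 0/3 or 1/5, though not in a cohort of four with no or one DLT. The 0.29-0.34 against 0.216 is an upper illustration: it takes the missed exposure as given and assigns a risk of 5-20%, and a patient who lost only one dose would probably sit closer to the combination rate. The averaged 0.23-0.25 rests on assumed miss rates of 5-10%. The documents give neither the DLT rates nor the frequency of missed pembrolizumab, so direction and mechanism are firmer than size. The remedy is cheap and belongs in place before Part B data are read.

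**What to change.** In Protocol 9.3 and SAP 5.4.1, add a minimum pembrolizumab exposure for DLT evaluability in Part B. The threshold is the sponsor's to set; mirroring the existing 75% is one option. State whether a stopped or partial infusion counts as a dose taken, otherwise the infusion-reaction case stays open. Keep patients who discontinue because of a DLT in the set whatever their exposure, and state that patients who fall short for non-DLT reasons are replaced.

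Sections 6.6 and 6.6.3 must be reconciled for the DLT observation period; which rule should apply is for the sponsor and investigators. It would also help to say explicitly that the three-evaluable minimum covers B1 and B2.

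The cost is about one clause in each document, the reconciliation of two sections, and the occasional replacement of a Part B patient.

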Abbreviations: AE = adverse event; C = Cycle; CTCAE = Common Terminology Criteria for Adverse Events; D = Day; ECG = electrocardiogram; ECHO = echocardiogram; ECOG = Eastern Cooperative Oncology Group; iRECIST = immuno-Response Evaluation Criteria in Solid Tumors; PK = pharmacokinetic; RECIST = Response Evaluation Criteria in Solid Tumors; Q3W = every 3 weeks.

Post-Treatment Follow-Up Schedule of Activities

Visit	Short-Term Follow-Up ^a			Long-Term Follow-Up ^b	Comments
	801	802	803	804-X	
Relative Day within Cycle	30-Day Follow-Up ± 5 days	60-Day Follow-Up ± 7 days	90-Day Follow-Up ± 7 days	(90 ± 14 Days)	
Physical exam	X				
Vital signs	X				Including weight, temperature, pulse rate, pulse oximetry, blood pressure, respiratory rate
ECOG performance status	X				
Radiologic imaging		X		X	Only for patients who discontinue study treatment without objectively measured progressive disease, continue to evaluate tumor response according to planned standard of care tumor assessment schedule until patient has objective disease progression or study completion.
Adverse events collection/CTCAE grading		X		X	CTCAE version 5.0. Collect AEs for 30 days following cessation of study treatment and SAEs for 90 days or 30 days following cessation of study treatment if the participant initiates new anticancer treatment, whichever comes first. Note: All pregnancies and exposure during breastfeeding must be reported, from time of treatment through 120 days following cessation of treatment, or 30 days following cessation of treatment.
Concomitant medication		X			All concomitant medications received up to 30 days after the last dose of study treatment should be recorded. Concomitant medications administered 30, 60, and 90 days after the last dose of study treatment should be recorded for SAEs and events of clinical interest.
Optional tumor biopsy	X				An optional tumor biopsy may be performed, if clinically feasible, after disease progression or at additional study time points, if warranted and agreed upon by the

Visit	Short-Term Follow-Up ^a			Long-Term Follow-Up ^b	Comments
	801	802	803	804-X	
Relative Day within Cycle	30-Day Follow-Up ± 5 days	60-Day Follow-Up ± 7 days	90-Day Follow-Up ± 7 days	(90 ± 14 Days)	
					investigator and Lilly.
Hematology	X				See Appendix 2.
Clinical chemistry	X				See Appendix 2.
Coagulation	X				PT or INR and aPTT should be collected at the mandatory Safety Follow-Up Visit after discontinuation of study therapy.

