4.1.1.2. Dose-Limiting Toxicity Determination

A DLT is defined as any of the events listed in the table below if the event occurs during the DLT observation period (2 Cycles/42 days for Cohorts A1-A6 and B1-B2) in Phase 1a, and toxicity that is not clearly and directly related to the primary disease or another etiology.

Patients who experience a DLT in the DLT observation period will be discontinued from study treatment.

Dose-Limiting Toxicities of Study Treatment

Hematologic Toxicity

 • Grade 3 thrombocytopenia associated with clinically significant bleeding and /or requiring platelet transfusion or Grade 4 thrombocytopenia of any duration • Grade ≥ 3 febrile neutropenia and/or neutropenia requiring G-CSF • Grade ≥ 4 neutropenia lasting >7 days • Grade ≥ 3 anemia requiring a blood transfusion • Other Grade 4 toxicity lasting >7 days, excluding toxicities listed below and Grade 3 endocrine irAEs that can be managed by steroids or hormone replacement therapy
Nonhematologic Toxicity – Nonlaboratory

 • Grade 4 AE (unless stated otherwise below) • Any Grade ≥ 3 colitis or noninfectious pneumonitis irrespective of duration • Any other Grade 3 AE, excluding toxicities listed below • Grade ≥ 3 toxicity lasting >7 days despite optimal supportive care • Other Grade 2 irAE, excluding colitis or pneumonitis, that:

 ○ does not downgrade to Grade 1 within 3 days after onset of the event despite optimal medical management including corticosteroid therapy, or ○ does not downgrade to Grade 1 or the patient's baseline level within 14 days after onset of the event
Nonhematologic Toxicity – Laboratory/Investigations

 • Grade 3 or 4 laboratory value if: 
 ○ Medical intervention or hospitalization is required to treat the patient, or ○ The abnormality persists for >7 days (excluding amylase and lipase) • ALT or AST: 
 ○ >8 × ULN ○ ≥2-fold above the patient's baseline value that lasts >7 days, if the patient has HCC or liver metastasis and had ALT or AST >3.0 × ULN at baseline ○ ≥3 × ULN with concomitant bilirubin >2 × ULN, in the absence of cholestasis • Total bilirubin >3 × ULN • Grade ≥3 amylase or lipase that is associated with symptoms or clinical manifestations of pancreatitis
Other Hematologic or Nonhematologic Toxicity

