6.5.1. Palliative Medicine and Supportive Care

The need for any form of radiotherapy (including palliative) in Cycles 1-2 will be cause for early discontinuation from the study. In Cycle 3 and beyond, palliative radiotherapy will be allowed if the parameters below are met.

Palliative radiation therapy is permitted after discussion with and agreement of the Lilly CRP/CRS or designee for irradiating small areas of painful metastases that cannot be managed adequately using systemic or local analgesics. Such areas must not be an identified target lesion and must not constitute progressive disease or meet RECIST/immuno-Response Evaluation Criteria in Solid Tumors (iRECIST) criteria for progressive disease. Any symptomatic deterioration or clinical disease progression requiring, in the opinion of the investigator, other forms of specific antitumor systemic therapy will be cause for discontinuation of study therapy.

In addition, any disease progression requiring other forms of specific antitumor therapy will also necessitate early discontinuation from the study. Appropriate documentation for all forms of

premedications, supportive care, and concomitant medications must be captured on the case report form (CRF). Replacement hormonal therapy initiated before study entry will be allowed.

Patients should receive full supportive care. Hematopoietic growth factors (eg, G-CSFs) may be administered according to institutional guidelines and the local Package Insert, except in the DLT observation period. Hematopoietic growth factors will be allowed in the DLT observation period if a patient experiences neutropenia that is declared an AE. Administration of G-CSFs prior to first occurrence of neutropenia is prohibited. Blood product transfusions are permitted throughout the study.

Prophylactic antibiotic treatment should be consistent with American Society of Clinical Oncology (ASCO) guidelines (Flowers et al. 2013).

If clinically indicated at any time during the study, erythropoietin and packed red blood cell transfusions may be used according to ASCO guidelines (Rizzo et al. 2008) with adherence to the local Package Insert. All concomitant medications should be recorded throughout the patient's participation in the study.

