10.5. Appendix 5: Creatinine Clearance Formula

Note: This formula is to be used for calculating creatinine clearance (CrCl) from **local laboratory results only**.

Patients aged ≥ 18 years

Cockcroft-Gault prediction of CrCl from serum creatinine (1976)

For serum creatinine concentration in mg/dL:

$$\text{CrCl} = \frac{(140 - \text{age}^a) \times (\text{wt}) \times 0.85 \text{ (if female), or } \times 1.0 \text{ (if male)}}{72 \times \text{serum creatinine (mg/dL)}} \text{ (mL/min)}$$

[figure not shown]
For serum creatinine concentration in $\mu\text{mol/L}$:

$$\text{CrCl} = \frac{(140 - \text{age}^a) \times (\text{wt}) \times 0.85 \text{ (if female), or } \times 1.0 \text{ (if male)}}{0.81 \times \text{serum creatinine } (\mu\text{mol/L})} \text{ (mL/min)}$$

^a Age in years, weight (wt) in kilograms.

Source: Cockcroft and Gault 1976.

10.6. Appendix 6: Dose-Finding Algorithm of the Modified Toxicity Probability Interval Method Showing Number of Patients Treated

The number of patients dosed at a given dose level is shown in the columns (X-axis), while the number of DLTs experienced is shown in the rows (Y-axis). The rules in this figure will be used for each dose level evaluated; the patient numbers and DLTs do not carry over from cohort to cohort. By locating the intersection of the number of patients dosed and the number of DLTs, 1 of 4 predefined rules is used:

- E: Escalate the dose
- S: Stay at the same dose
- D: De-escalate the dose
- DU: De-escalate the dose due to unacceptable toxicity. The dose cannot be re-escalated to this dose level at a future point in the escalation.

For example, within a cohort:

- If 1 of 3 patients experiences a DLT, stay at the same dose (see “S” in column 3, row 1). The fourth patient must be treated at the same dose level.
- If 1 of 6 patients experiences a DLT, escalate the dose (see “E” at column 6, row 1).
- If 2 of 3 patients experience a DLT the dose to treat the next patient is de-escalated (see “D” at column 3, row 2). If 5 of 7 patients experience a DLT, the dose is determined to be unacceptably toxic and will never be used again in the trial (see “DU” at column 7, row 5).

The final MTD will be determined when all patients complete DLT evaluation. A hypothetical example for the MTD determination is shown below for illustration (based on the pre-specified parameters, number of DLTs, and number of DLT-evaluable patients).

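### The DLT-evaluable definition has no place for a patient who stops for another reason and then has a DLT inside the 42-day window

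*Protocol*

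**What the plan says.** Protocol 4.1.1.2 makes a listed toxicity a DLT "if the event occurs during the DLT observation period (2 Cycles/42 days for Cohorts A1-A6 and B1-B2) in Phase 1a". Nothing there requires the patient to be on treatment at onset. The same section adds: "Patients who experience a DLT in the DLT observation period will be discontinued from study treatment".

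Protocol 9.3 gives two routes into the DLT-evaluable set. Route 1 is "All treated patients who have completed 2 cycles (6 weeks) of treatment (having taken at least 75% of the planned doses of LY3435151"). Route 2 is "or have discontinued treatment due to a DLT". SAP 5.4.1 has the same definition.

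Appendix 6 describes the columns of the decision grid as patients dosed and the rows as DLTs experienced. It then says that the MTD illustration is "based on the pre-specified parameters, number of DLTs, and number of DLT-evaluable patients", while the table under that illustration counts patients treated. Sections 4.1.1 and 4.1.1.1 set the minimum size of Cohorts A2 to A6 at three evaluable patients.

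**The concern.** The DLT definition depends on event and time. Route 2 depends on why treatment stopped. The two agree for a DLT that arises on treatment, because it forces discontinuation. They part when treatment has already ended for another reason.

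The protocol foresees such stops. Section 6.5.1 says: "The need for any form of radiotherapy (including palliative) in Cycles 1-2 will be cause for early discontinuation from the study". Section 7.1 adds progression and participant decision. Section 6.6 expects immune-related events to be possible months after the last dose. A patient could have the Cycle 1 dose, stop on Day 20 and develop Grade 3 colitis on Day 30. That is a DLT under 4.1.1.2 in a patient whom 9.3 calls non-evaluable.

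DLTs are a primary Phase 1a endpoint and drive the mTPI-2 rule. With three to seven patients at a dose level, the handling of one patient can decide the next step.

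**Working it through.** **1. Does the patient enter by either route?** Two doses are planned in 42 days, and 75% of 2 is 1.5, so both are needed. One of two is 50%: route 1 fails. The stop came before the DLT and had another cause: route 2 fails. This is clearest for a stop before the second dose. After the Cycle 2 Day 1 dose, whether two cycles were completed is open to interpretation.

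**2. Does other text restore the patient?**
- Section 4.1.1.3 reserves the DLT-equivalent category in Phase 1a for events outside the DLT assessment period.
- Section 4.1.1.2 has adverse events of non-evaluable patients reviewed, but writes this for confounded cases and does not return them to the count.
- Sections 4.1.1.4 and 9.5 provide for review and judgment on all the data, not for a change to the evaluable set.

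**3. Reproduce the plan's decisions.** Stated inputs: target 0.30, equivalence interval 0.25 to 0.35. Assumed: Beta(1,1) prior, sub-intervals of width 0.10, and DU when P(p > 0.30) exceeds 0.95. For x DLTs in n patients the posterior is Beta(1+x, 1+n−x). The unit probability mass of an interval is its posterior probability divided by its width, and the largest one gives the decision.

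This reproduces 1/3 S, 1/6 E, 2/3 D and 5/7 DU (Appendix 6), 2/6 S (4.1.1.1), and 1/5 E (the Cohort A1 rule in 4.1.1). The grid itself is a missing figure and was not checked cell by cell.

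**4. Add the omitted patient.** Each turns x/n into (x+1)/(n+1).

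| Without the patient | With the patient |
|---|---|
| 0/3 E | 1/4 S |
| 1/3 S | 2/4 D |
| 2/3 D | 3/4 DU |
| 1/5 E | 2/6 S |
| 1/6 E | 2/7 S |
| 2/6 S | 3/7 D |

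Largest escalation mass against the stay mass: 0/3, 3.71 v 1.38; 1/4, 2.02 v 2.04; 1/6, 2.72 v 2.11; 2/7, 2.16 v 2.51. The 1/4 result is close, so it is the one most sensitive to the assumed prior.

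**5. Effect on the MTD.** The illustration in Appendix 6 (0/1, 0/3, 0/3, 1/6, 0/3, 2/3; MTD at level 5) reproduces with isotonic regression and ties to the higher dose. An omitted DLT at level 5 (0/3 to 1/4) leaves it at level 5.

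Now suppose level 6 had 2/6. With near-raw rates, levels 4 and 5 pool to 1/9 = 0.11. Level 6 is 0.33, below the 0.35 limit and closer to 0.30, so the MTD is level 6. With the omitted patient it is 3/7 = 0.43, above 0.35, and the MTD is level 5. Under a Beta(1,1) prior level 6 is 3/8 = 0.375 or 4/9 = 0.44, both above 0.35, and the MTD is level 5 either way. The shift depends on the estimator, which the documents do not state.

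**6. Would the event be recorded?** The follow-up schedule says: "Collect AEs for 30 days following cessation of study treatment". If cessation is the decision to stop, a stop on Day 12 or later reaches Day 42 (12 + 30). If it is the last dose, a single Day 1 dose gives collection to about Day 31 for non-serious events. Serious events are collected for 90 days, or 30 days once new anticancer treatment starts. The Day 30 example falls inside either reading.

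**The case against.** **The escalation grid is labelled by patients dosed.** On that reading, four dosed with one DLT is already 1/4, stay. This stands: the change of decision is conditional. But the MTD sentence in the same appendix and the cohort minimum use evaluable patients, so this reading exposes a conflict and does not remove it. Nor is the number of DLTs expressly limited to evaluable patients; counting the event while leaving out the patient would mismatch numerator and denominator.

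**Observed DLTs are considered elsewhere.** Section 4.1.1 bases the RP2D on observed DLTs and expands Cohort A1 if a patient has one, with no evaluability condition. A review meeting follows each cohort, and a more conservative choice than the rule is allowed. This also stands. A reader might infer that the trial would escalate past a recorded DLT unnoticed; the documents do not support that.

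**The exclusion is not one-sided.** A reader might infer that the clause removes only evidence of toxicity and so biases the rate downward. It also removes every early stopper without a DLT, so neither inference holds. Illustration with assumed figures: 15% have a DLT before Day 20, later risk is 17.65%, and 20% of those still DLT-free stop at Day 20.
- True rate if post-stop risk is the same: 0.15 + 0.85 × 0.1765 = 0.30.
- Current rule: (0.15 + 0.85 × 0.80 × 0.1765) / (0.15 + 0.85 × 0.80) = 0.27/0.83 = 0.325.
- Revised clause: 0.30/0.86 = 0.349.

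Here the current rule already overestimates. It would underestimate only if post-stop risk q satisfied 0.27 + 0.17q > 0.325, that is q above about 0.325.

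**The case is uncommon.** On-treatment DLTs are captured, and scans come every six weeks, so scheduled imaging should prompt few stops before Day 42. The documents give no frequency.

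**Conclusion.** The point holds in a narrow form. As written, both documents exclude from the DLT-evaluable set a patient whose event the protocol itself defines as a DLT, and no other text returns that patient to the set. Appendix 6 uses two descriptions of the denominator.

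If evaluable patients are counted, one such patient can move the rule by one step at the cohort sizes planned. It can move the MTD by one level under near-raw rates, though not in the Beta(1,1) check. If patients dosed are counted, Appendix 6 conflicts with its own MTD sentence.

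The decisions rest on the assumed Beta(1,1) prior. How often the case would arise is unknown. The defect is in the rule-based count for a primary endpoint; the RP2D discussion can still take the event into account by judgment.

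**What to change.** In Protocol 9.3 and SAP 5.4.1, replace route 2 with wording to this effect: or have experienced a DLT during the DLT observation period, before any new anticancer therapy, whatever the reason for stopping treatment.

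In Appendix 6, state that the decision grid and the MTD both use DLT-evaluable patients, and label the illustration to match.

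In the follow-up schedule, say whether cessation of study treatment means the decision to stop or the last dose. Non-serious event capture to Day 42 depends on it. If it means the last dose, complete capture after a single dose would need collection to Day 42, which is a small amount of added data.

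The cost is one clause in each document and a clarification in Appendix 6 and the schedule. No DLT criterion or treatment rule changes. The downside is that early stoppers then count only if they have a DLT, so the estimated rate can be somewhat higher (0.349 against 0.325 in the illustration above). That error is on the cautious side, and the SAP should acknowledge it.
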